## 1.0 Background

Sinus node dysfunction is highly prevalent among patients with congenital heart disease, manifesting as resting bradycardia or chronotropic incompetence. As children and adults with congenital heart disease are now expected to have increasing lifeexpectancy; with well over 1 million adult patients currently living in North America, issues such as mental health, acquired comorbidities and their impact on overall cardiovascular health have assumed increased scrutiny.

It is now understood that objective measures of aerobic capacity, such as peak  $\dot{V}O_2$ , peak VENC $\dot{O}_2$ , and heart rate reserve predict all-cause mortality for adult patients with congenital heart disease. As the chronotropic response during exercise is a key determinant of aerobic capacity, improvement in sensor-based technology for heart rate support is expected to have a significant impact on functional capacity and longevity in this population. Some forms of congenital heart disease, such as single ventricle physiology after the Fontan population are especially likely to benefit, as cardiac output is determined almost exclusively by heart rate during exertion due to limited ability to augment cardiac stroke volume.

It is also becoming increasingly clear that sedentary behaviors are highly relevant to overall cardiovascular health in the general adult population. Adult patients with congenital heart disease are at especially high risk for sedentary behavior as a result of 1) chronic restriction for physical activities based on ill-founded medical advice, 2) chronotropic incompetence resulting from prior surgical palliations and hemodynamic stressors, and 3) overestimation of physical activity.

The closed-loop stimulation (CLS) algorithm developed by Biotronik Inc. is a novel sensor-based technology that relies on the change in myocardial systolic impedance for modulation of the heart rate during physical and emotional stress. The pacing algorithm has been shown to be highly effective for a wide range of clinical scenarios. Despite the fact that congenital heart disease (CHD) patients are likely to derive significant benefit in terms of functional ability and aerobic capacity using this novel technology, the CLS system has not been adequately studied in this population. As many CHD patients also undergo epicardial placement of pacing systems at the time of concomitant cardiac surgery, CLS has been less often utilized in this population given almost no data in the setting of surgical electrode placement. The present study intends to examine the benefits of the Biotronik CLS algorithm in the CHD population, employing the use of epicardial pacemaker systems in the study protocol.

## 2.0 Rationale and Specific Aims

Improvement in sensor-based rate adaptation for sinus node dysfunction is needed in the CHD population. Emerging data suggest that greater aerobic capacity and heart rate

reserve are independently associated with superior outcomes in this population. Improvements in these parameters can be expected with the use of the Biotronik CLS algorithm and this pacing system may therefore be particularly well-suited to patients with CHD.

The Specific Aims of this protocol are:

Primary Aim: To determine the performance of CLS for CHD patients after both transvenous and epicardial pacemaker implantation

Hypothesis: CLS after either pacemaker implantation strategy will result in equivalent improvements in autonomic control of chronotropic response as compared to standard sensor based rate modulation

Primary outcome: Objective change in autonomic modulation of heart rate while randomized to CLS pacing with mental stress and ANSAR testing

Secondary outcomes: Increase in aerobic capacity, non-sedentary behavior, and quality of life while randomized to CLS pacing

This will be a single-blind (blinded subjects) randomized cross-over study, in which each patient will receive treatment A (CLS-on or CLS-off) for 3 months followed by treatment B (CLS-0ff or CLS-on).

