## Randomization

[figure not shown]
There will be a 50:50 randomization, with half the subjects randomized to CLS-on then CLS-off, and half randomized to CLS-off then CLS-on.

Subjects previously receiving rate-responsive pacing with CLS that are randomly selected to CLS-on will continue with the identical programmed parameters. For subjects not previously receiving rate-responsive pacing with CLS that are randomly selected to CLS-on nominal programming will be utilized with a base rate of 60 beats per minute.

Subjects will then initiate treatment A (CLS-on or CLS-off) in a blinded fashion. During the testing period, subjects will be tracked with the implanted device accelerometer to quantify physical activity. At 3 months, all subjects will undergo testing as noted below.

- 24 hour Holter monitoring with spectral analysis
- Cycle-ergometer stress with cardiopulmonary gas exchange analysis
- Free form activities with cardiopulmonary gas exchange analysis (staircase, walking, sweeping, suitcase lifting with right and left arms, etc.)
- ANSAR testing (hand grip, Valsalva, deep breathing, and orthostatic challenge)
- Mental stress test with continuous electrocardiographic recording
- Quality of life questionnaire (SF-36/Somerville index)

After 3 months of treatment A, subjects will be reprogrammed to treatment B. Tracking of physical activity with the device accelerometer will continue during this period. After 3 months of treatment B, repeat testing will be repeated as described above. At the conclusion of the study, patients will be asked which pacing mode is preferred.

Patients will be followed during both treatment phases per usual clinical routine. Patients who experience significant symptoms (extreme fatigue, debilitating palpitations, or other clinically relevant symptoms) will be evaluated by their treating physician. Subjects that have any adverse events during treatment A will discontinue treatment A and immediately crossover to treatment B. Subjects with events during treatment B will be removed from the study and unblinded. Further treatment will be determined by the treating physician.

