#### 10.0 Statistical Considerations

##### Sample Size Estimation and Power Analysis

The primary endpoint of this randomized controlled 2x2 cross-over trial will be to measure the influence of autonomic function on heart rate response, and to show an equivalent response for both epicardial and transvenous CLS pacemaker systems. The objective of this study is to evaluate changes in heart rate in response to the CLS algorithm versus a standard accelerometer during various tests of autonomic function. Previous studies of adults with chronotropic incompetence using the CLS algorithm have demonstrated a mean increase in heart rate of  $16.1 \pm 1.1$  beats/minute during mental stress with CLS-on versus  $5.8 \pm 0.6$  beats/minute with standard accelerometer ( $p<0.001$ ).

A further pilot study using ANSAR demonstrated a mean increase in 12.5 beats/minute during isometric hand-grip with CLS-on versus 2.9 beats/min with standard accelerometer ( $p=0.004$ ), 13.2 beats/minute during deep breathing versus 2.9 beats/minute ( $p=0.004$ ), 16.0 beats/minute during Valsalva maneuver versus 4.5 beats/minute ( $p=0.004$ ), and 14.9 beats/minute for postural change versus 6.2 beats/minute ( $p=0.039$ ). The results of the prior pilot study are summarized below.

ANSAR HEART RATE	Baseline	DOD-CLS	DDD	T test	Wilcoxon test
Resting	55.8	70.0	60.8	<0.001	0.004
Isometric Handgrip	59.4	71.9	62.3	<0.001	0.004
Deep Breathing	58.0	71.2	60.9	<0.001	0.004
Valsalva maneuver	57.1	73.1	61.6	<0.001	0.004
Postural Change	58.1	73.0	64.3	0.015	0.039

From Pavri et al. Circulation 2006;114;II 749. 

A two-sided t-test achieves 80% power to infer that the mean difference is not 0 when the total sample size of a cross-over design is 40 (or 81% when n=24 and 96% when n=30) assuming a 5% type I error. The actual difference and the square root of the within mean square error are assumed to be 10. Considering a drop-out rate of 30%, a total of 57 patients will need to be enrolled to achieve the target sample number.

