## Statistical Analysis Plan

Descriptive statistics, including means, standard deviations, and ranges for continuous variables, as well as percentages and frequencies for categorical variables, will be provided to describe the study sample. Differences between group means for continuous variables will be examined using ANOVA or Kruskal-Wallis Test. Point estimates along with the corresponding p-values and 95% confidence intervals will be reported. The adjusted p-values and the corresponding 95% confidence interval will be reported for multivariate analyses. Statistical analysis will be done with JMP version 12.0 (SAS Corporation, Cary, NC).

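### The primary outcome covers five heart-rate contrasts with no deciding contrast, success rule or multiplicity method, so the stated 5% type I error is not secured

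*Combined protocol and SAP*

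**What the plan says.** - **Primary outcome (section 2.0):** "Objective change in autonomic modulation of heart rate while randomized to CLS pacing with mental stress and ANSAR testing". It is worded as one outcome and read on more than one test.
- **Tests done at the end of each period (section 6.0, Randomization):** "ANSAR testing (hand grip, Valsalva, deep breathing, and orthostatic challenge"), and as its own item "Mental stress test with continuous electrocardiographic recording". That is four manoeuvres plus one.
- **Objective (section 10.0, Sample Size Estimation and Power Analysis):** to evaluate "changes in heart rate in response to the CLS algorithm versus a standard accelerometer during various tests of autonomic function". The number and order of these tests are not given. The same paragraph adds a further aim, "to show an equivalent response for both epicardial and transvenous CLS pacemaker systems".
- **Sample size (same section):** "A two-sided t-test achieves 80% power to infer that the mean difference is not 0", for one mean difference, "assuming a 5% type I error". The difference and the root within mean square error are both set at 10. The stated power is 80% at N=40, 81% at N=24 and 96% at N=30.
- **Analysis (Statistical Analysis Plan):** ANOVA or Kruskal-Wallis, and "Point estimates along with the corresponding p-values and 95% confidence intervals will be reported". Adjusted p-values are mentioned once, for multivariate analyses. No multiplicity procedure is named.

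**The concern.** The 5% belongs to a single test, but the outcome it is meant to protect has five components. The plan does not say whether one component decides, whether they are combined, or whether any or all must be positive. Two readers could therefore follow the plan faithfully and disagree on whether the primary outcome was met.

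Without a rule, one significant manoeuvre out of five could be reported as success, and the stressor to feature could be chosen after the data are seen. The prior results in section 10.0 lean that way: they are given stressor by stressor, each with its own p-value.

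**Working it through.** **1. The plan's own power figure.** For a 2x2 cross-over, the standard error is root MSE × √(2/N), with N − 2 degrees of freedom, and power comes from the noncentral t distribution (two-sided 5%). With difference 10 and root MSE 10, the noncentrality is 10 / (10 × √(2/N)) = √(N/2).

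| N | Noncentrality | Power at 5% | Plan states |
|---|---|---|---|
| 24 | 3.46 | 91.1% | 81% |
| 30 | 3.87 | 96.2% | 96% |
| 40 | 4.47 | 99.2% | 80% |

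Only the N=30 figure is reproduced. On these inputs 80% is reached at N=18 (80.4%). The stated figures also conflict with each other, since power is higher at 24 and 30 than at 40. Reading the design as two parallel groups gives 86.9% at N=40, so that does not recover 80% either.

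**2. Number of contrasts.** Mental stress (1) + hand grip, Valsalva, deep breathing and orthostatic challenge (4) = 5.

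**3. Type I error under each rule the wording allows.**

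- One named contrast, or one combined measure, at 5%: 5%.
- All five must be significant at 5%: at most 5%.
- Any one of five at 5%, independent: 1 − 0.95^5 = 22.6%. The upper bound is 5 × 5% = 25%.
- Any one of five at 5%, with equally correlated normal test statistics:

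| Assumed correlation | Family-wise error |
|---|---|
| 0.3 | 20.9% |
| 0.5 | 18.3% |
| 0.7 | 14.8% |
| 0.9 | 10.2% |

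The documents give no correlation between stressors, so these values are assumptions. Across the range the error is about two to four and a half times 5%.

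**4. Sensitivity to the count.** Taking mental stress and ANSAR as two tests gives 1 − 0.95^2 = 9.75% under independence. Counting the resting row of the pilot table as a sixth contrast gives 1 − 0.95^6 = 26.5%.

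**5. Power cost of Holm across five.** The strictest step is 0.05/5 = 0.01.

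- On the stated inputs, power per contrast at 1% is 95.5% at N=40 (against 99.2% at 5%), 85.7% at N=30 and 73.4% at N=24.
- If instead the stated 80% at N=40 is right and an input is wrong, the noncentrality that gives 80% at 5% with 38 degrees of freedom is about 2.87. Against the 1% critical value of 2.71, power is then about 57%.

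**The case against.** The strongest reply is that no section says the five contrasts are each tested at 5%. The 5% appears once, for one t-test, and the analysis section is generic. A reader might infer that the trial's type I error is 22.6%, or at least that it exceeds 5%. The documents do not support that: section 2.0 words a single outcome, and a composite or an all-must-succeed rule would fit it and hold the error at or below 5%. Nor does the analysis section say that an unadjusted p-value will be given for every stressor. It does not define its adjusted p-values; covariate adjustment is the likelier meaning, but that too is an inference.

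It can also be said that independence is implausible, because all stressors are measured in the same patients under the same pacing mode, and that the count of five is not fixed.

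All of this stands, and it limits the claim to an error rate that is undetermined. It does not remove the gap. Neither a composite nor an all-must-succeed rule is written anywhere, and the only pattern the documents display is one p-value per stressor.

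**Conclusion.** The point holds as a failure to secure the stated error rate, not as a demonstrated excess. The plan sizes one test at 5% and applies it to an outcome with five components and no rule for deciding success.

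The inflation of about 10% to 23% rests on three assumptions: that any one significant stressor counts as success, that there are five contrasts, and that correlations run from 0.9 down to zero. The first is the natural reading of separate p-values but is not stated.

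The cost of Holm across five cannot be settled from the documents, because the stated power at N=40 does not follow from the stated inputs. The case for naming one primary contrast does not depend on which of them is right. The gap should be closed before data are analysed.

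**What to change.** Amend the primary outcome in section 2.0 and the Statistical Analysis Plan in one of two ways.

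1. **Single primary contrast (preferred).** Name the mental-stress heart-rate rise, CLS-on versus CLS-off, as the primary contrast at two-sided 5%. Test the four ANSAR manoeuvres with Holm only if it succeeds. This costs no power on the primary contrast. The downside is that no ANSAR claim is possible if mental stress fails.
2. **Holm across all five.** Claim the primary outcome only for stressors with a Holm-adjusted p-value below 0.05. Power per contrast at the strictest step is 95.5% or about 57% at N=40, depending on which part of the sample-size paragraph is correct.

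Either is a sentence or two of text, with no added tests or visits. Under the second option, whether 40 completers suffice cannot be judged until the inputs and power figures in section 10.0 are reconciled.

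Neither option covers epicardial versus transvenous equivalence, which section 10.0 also places in the primary endpoint. That comparison needs its own margin and its own place in the testing plan.

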## 5.0 Enrollment]Randomization

Patient Enrollment: The treating physician will identify potential subjects with a previously implanted Biotronik pacemaker and present a brief overview of the study; if the subject is interested, the study will be described in detail. Informed consent will be obtained by the investigator after discussing the study, including the voluntary nature of participation and notification the subject can withdraw at any time. Ample time for questions and answers will be allowed. The investigator will give the subject and his/her legal guardian the opportunity to take the consent home to think about it more, with the option to call or meet with the investigator to ask additional questions. If the subject and/or his/her parent/legal guardian agree to participate, the investigator will ask them to sign a written, informed consent and assent. A copy of the assent and consent will be given to the subject and/or his/her parent/legal guardian.

Randomization Procedure: This will be a single-blind placebo-controlled randomized crossover study with 2 treatments: CLS-on versus CLS-off (accelerometer only). Each enrolled patient will receive both treatments for 3 months. The order of treatments will be randomized 1 :1.

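### Only subjects are blinded: with testers and readers unmasked and no fixed reading rule or effort script, knowledge of the pacing mode could bias the CLS-versus-accelerometer contrast, mainly for aerobic capacity and preference

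*Combined protocol and SAP*

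**What the plan says.** Section 2.0 sets the level of blinding: "This will be a single-blind (blinded subjects) randomized cross-over study". Section 5.0 again calls the trial single-blind and names no further blinded role. Under Randomization in section 6.0, the conduct is described the same way: "Subjects will then initiate treatment A (CLS-on or CLS-off) in a blinded fashion".

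The main outcome is in section 2.0: "Primary outcome: Objective change in autonomic modulation of heart rate while randomized to CLS pacing with mental stress and ANSAR testing". Exercise capacity, activity level and quality of life are listed there as secondary.

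The tests, done at the end of each 3-month period, are listed in section 6.0. They include the four ANSAR manoeuvres (hand grip, Valsalva, deep breathing, orthostatic challenge), "Mental stress test with continuous electrocardiographic recording" and "Cycle-ergometer stress with cardiopulmonary gas exchange analysis". The same section adds: "At the conclusion of the study, patients will be asked which pacing mode is preferred".

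Neither the protocol sections nor the Statistical Analysis Plan says who runs or reads these tests, whether those people know the mode, which stretch of the recording gives the heart rate, what it is compared with, or how patients are encouraged.

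**The concern.** Calling the primary outcome objective covers how heart rate is recorded. It does not cover how the response is provoked or how a value is taken from the recording. Hand grip, Valsalva and cycle exercise depend on effort, and effort can respond to encouragement. A continuous ECG yields a single heart-rate value only after someone has chosen a window and a reference. If the people doing these things know the mode, their handling could differ between modes without any intent.

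The cross-over protects against differences between patients and, with balanced order, against period effects. It does not protect against a bias tied to the mode, because every patient is tested once in each mode and the bias goes straight into the difference. Sections 1.0 and 2.0 state an expectation that CLS will help, so a sceptical reader would ask how the readings were shielded from it. If the plan has no answer, a reported gain in aerobic capacity or a preference for CLS could be disputed.

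**Working it through.** **1. Who is masked.** Sections 2.0, 5.0 and 6.0 agree: subjects, and nobody else is named. That staff know the mode, and that they coach or choose segments, is inferred from this silence and from the nature of the tests.

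**2. Where a mode-related bias goes.** Let d be the true CLS-minus-accelerometer difference and b a constant bias that follows the mode.

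- Within-patient contrast: expected value d + b. Randomizing the order does not remove b.
- Route comparison (section 10.0): (d_epicardial + b) − (d_transvenous + b) = d_epicardial − d_transvenous. A constant b cancels, and only a bias that differs by route would remain.

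**3. The plan's heart-rate figures.** The pilot table in section 10.0 reproduces the increases in its text when each is taken from the Baseline column.

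| Manoeuvre | CLS − Baseline | DDD − Baseline | Contrast |
|---|---|---|---|
| Hand grip | 71.9 − 59.4 = 12.5 | 62.3 − 59.4 = 2.9 | 9.6 |
| Deep breathing | 71.2 − 58.0 = 13.2 | 60.9 − 58.0 = 2.9 | 10.3 |
| Valsalva | 73.1 − 57.1 = 16.0 | 61.6 − 57.1 = 4.5 | 11.5 |
| Postural change | 73.0 − 58.1 = 14.9 | 64.3 − 58.1 = 6.2 | 8.7 |

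Mental stress in the cited earlier study gives 16.1 − 5.8 = 10.3. The planned difference is 10. Against 10, an assumed bias of 1 to 2 beats/min is 10% to 20% of the effect.

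**4. Why the reference must be fixed.** Measured instead from each mode's own Resting value (70.0 with CLS, 60.8 with DDD), the contrasts are:

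- hand grip: 1.9 − 1.5 = 0.4
- deep breathing: 1.2 − 0.1 = 1.1
- Valsalva: 3.1 − 0.8 = 2.3
- postural change: 3.0 − 3.5 = −0.5

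The plan's text uses the Baseline column for the pilot but does not say which reference the trial will use. An open choice of this size should not be left to someone who knows the mode.

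**5. Illustration with assumed biases.** Take the plan's within-subject SD of 10 and n = 40, no true effect, and a two-sided 5% test. The standard error is 10 × √(2/40) = 2.24 beats/min, with 38 degrees of freedom. From the noncentral t distribution:

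| Assumed bias (beats/min) | False-positive rate |
|---|---|
| 1 | 7% |
| 2 | 14% |
| 3 | 26% |
| 5 | 59% |

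This shows how the test reacts to a bias. It is no evidence that one exists. Only the SD and n are borrowed from section 10.0; whether its power figures follow from them is a separate matter.

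**6. Aerobic capacity and preference.** Section 10.0 gives no expected difference or SD for aerobic capacity and no planning figure for preference, so no size can be computed for either.

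**The case against.** Single-blinding is openly stated, and much of the outcome set is well protected. Heart rate is recorded by instrument in patients with more than 70% atrial pacing. Deep breathing and orthostatic challenge are less plausibly driven by encouragement. Activity comes from the implanted accelerometer, and quality of life is reported by blinded subjects. Aerobic capacity is secondary, and preference is not among the outcomes listed in section 2.0. All of this stands, and it is why heart rate is not the most exposed outcome.

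It is also fair that masking readers would be incomplete. Resting rates of 70.0 with CLS and 60.8 with DDD in the pilot suggest that the trace itself may disclose the mode. That limits what coded files can achieve. It does not weaken the case for a fixed reading rule and a common script, which work whether or not the reader guesses.

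A reader might go further and infer that unmasked staff will push results towards CLS, or that 1 to 2 beats/min would match the heart-rate response itself. The documents support neither. They give no direction, and the small rises of 0.1 to 3.5 beats/min appear only with the Resting row as reference, whereas section 10.0 measures from Baseline. Nor do they say that the preference question is put in person, or that the Holter recording, which is specified with spectral analysis, feeds the primary outcome through a reader-chosen window.

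**Conclusion.** The concern holds as a possible bias that is cheap to reduce. The plan leaves testers and readers unmasked and does not fix how heart rate is read or effort encouraged, so knowledge of the mode could enter the CLS-versus-accelerometer contrast. Exposure is greatest for cycle-ergometer aerobic capacity and for preference. It is smaller for heart rate: if the trial uses the pilot's Baseline reference and the difference is near 10 beats/min, a bias of 1 or 2 beats/min is unlikely to create the result alone.

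The conclusion rests on two assumptions: that staff can learn the mode, and that effort and reading leave them some discretion. Both are reasonable, and neither is stated in the plan. The actual size and direction of any bias cannot be derived.

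**What to change.** Amend the protocol before further tests are run or read:

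1. Store ECG, ANSAR and gas-exchange files under a visit code. Read them by a rule written in advance, with the same window and the same reference for both modes, before the mode is linked.
2. Use one encouragement script for the effort-dependent tests in both periods.
3. Do not tell test staff the mode, where current staffing allows. The documents do not describe staffing, so a strict split between the person who programs the device and those who test cannot be assumed.
4. Ask preference as first or second period, before unblinding. Subjects removed during treatment B or withdrawing are unblinded under sections 6.0 and 9.0, so for them the order of these steps needs stating.

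The cost is protocol wording, coded file names and a written script, with no added visit, procedure or patient. The downside is imperfect masking, since the paced rate may show the mode in the room or on the trace. Most of the gain therefore comes from the fixed reading rule and the common script. Uneven coaching cannot be repaired at analysis.
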